8.4.7 Other Analyses

8.4.7.1 Immunogenicity Analyses

Immunogenicity may be reported for ADA positive status (such as persistent positive, neutralizing positive, only last sample positive, baseline positive and other positive) and ADA negative status, relative to baseline. Effect of immunogenicity on safety, efficacy, biomarkers and PK may be explored. Additional details will be described in the SAP.

8.5 Interim Analyses

No formal interim analysis is planned. Interim analyses may be conducted if it is necessary in order to make decisions regarding further development. Summaries and listings of efficacy and safety will be provided. Interim analyses will not impact the study conduct and the trial will continue as planned.

9 STUDY MANAGEMENT

9.1 Compliance

9.1.1 Compliance with the Protocol and Protocol Revisions

The study shall be conducted as described in this approved protocol. All revisions to the protocol must be discussed with, and be prepared by, BMS. The investigator should not implement any deviation or change to the protocol without prior review and documented approval/favorable opinion from the IRB/IEC of an amendment, except where necessary to eliminate an immediate hazard(s) to study subjects.

If a deviation or change to a protocol is implemented to eliminate an immediate hazard(s) prior to obtaining IRB/IEC approval/favorable opinion, as soon as possible the deviation or change will be submitted to:

- IRB/IEC for review and approval/favorable opinion
- BMS
- Regulatory Authority(ies), if required by local regulations

Documentation of approval signed by the chairperson or designee of the IRB(s)/IEC(s) must be sent to BMS.

If an amendment substantially alters the study design or increases the potential risk to the subject: (1) the consent form must be revised and submitted to the IRB(s)/IEC(s) for review and approval/favorable opinion; (2) the revised form must be used to obtain consent from subjects

currently enrolled in the study if they are affected by the amendment; and (3) the new form must be used to obtain consent from new subjects prior to enrollment.

If the revision is done via an administrative letter, investigators must inform their IRB(s)/IEC(s).

9.1.2 Monitoring

BMS representatives will review data centrally to identify potential issues to determine a schedule of on-site visits for targeted review of study records.

Representatives of BMS must be allowed to visit all study site locations periodically to assess the data quality and study integrity. On site they will review study records and directly compare them with source documents, discuss the conduct of the study with the investigator, and verify that the facilities remain acceptable.

In addition, the study may be evaluated by BMS internal auditors and government inspectors who must be allowed access to CRFs, source documents, other study files, and study facilities. BMS audit reports will be kept confidential.

The investigator must notify BMS promptly of any inspections scheduled by regulatory authorities, and promptly forward copies of inspection reports to BMS.

9.1.2.1 Source Documentation

The Investigator is responsible for ensuring that the source data are accurate, legible, contemporaneous, original and attributable, whether the data are hand-written on paper or entered electronically. If source data are created (first entered), modified, maintained, archived, retrieved, or transmitted electronically via computerized systems (and/or any other kind of electronic devices) as part of regulated clinical trial activities, such systems must be compliant with all applicable laws and regulations governing use of electronic records and/or electronic signatures. Such systems may include, but are not limited to, electronic medical/health records (EMRs/EHRs), adverse event tracking/reporting, protocol required assessments, and/or drug accountability records).

When paper records from such systems are used in place of electronic format to perform regulated activities, such paper records should be certified copies. A certified copy consists of a copy of original information that has been verified, as indicated by a dated signature, as an exact copy having all of the same attributes and information as the original.

9.1.3 Investigational Site Training

Bristol-Myers Squibb will provide quality investigational staff training prior to study initiation. Training topics will include but are not limited to: GCP, AE reporting, study details and procedure, electronic CRFs, study documentation, informed consent, and enrollment of WOCBP.

9.2 Records

9.2.1 Records Retention

The investigator must retain all study records and source documents for the maximum period required by applicable regulations and guidelines, or institution procedures, or for the period specified by BMS, whichever is longer. The investigator must contact BMS prior to destroying any records associated with the study.

BMS will notify the investigator when the study records are no longer needed.

If the investigator withdraws from the study (eg, relocation, retirement), the records shall be transferred to a mutually agreed upon designee (eg, another investigator, IRB). Notice of such transfer will be given in writing to BMS.

9.2.2 Study Drug Records

It is the responsibility of the investigator to ensure that a current disposition record of study drug (inventoried and dispensed) is maintained at the study site to include investigational product and the following non-investigational product(s). Records or logs must comply with applicable regulations and guidelines and should include:

- amount received and placed in storage area
- amount currently in storage area
- label identification number or batch number
- amount dispensed to and returned by each subject, including unique subject identifiers
- amount transferred to another area/site for dispensing or storage
- nonstudy disposition (eg, lost, wasted)
- amount destroyed at study site, if applicable
- amount returned to BMS
- retain samples for bioavailability/bioequivalence, if applicable
- dates and initials of person responsible for Investigational Product dispensing/accountability, as per the Delegation of Authority Form.

BMS will provide forms to facilitate inventory control if the investigational site does not have an established system that meets these requirements.

9.2.3 Case Report Forms

An investigator is required to prepare and maintain adequate and accurate case histories designed to record all observations and other data pertinent to the investigation on each individual treated or entered as a control in the investigation. Data that are derived from source documents and reported on the CRF must be consistent with the source documents or the discrepancies must be explained. Additional clinical information may be collected and analyzed in an effort to enhance

understanding of product safety. CRFs may be requested for AEs and/or laboratory abnormalities that are reported or identified during the course of the study.

For sites using the BMS electronic data capture tool, electronic CRFs will be prepared for all data collection fields except for fields specific to SAEs and pregnancy, which will be reported on the paper or electronic SAE form and Pregnancy Surveillance form, respectively. Spaces may be left blank only in those circumstances permitted by study-specific CRF completion guidelines provided by BMS.

The confidentiality of records that could identify subjects must be protected, respecting the privacy and confidentiality rules in accordance with the applicable regulatory requirement(s).

The investigator will maintain a signature sheet to document signatures and initials of all persons authorized to make entries and/or corrections on CRFs.

The completed CRF, including any paper or electronic SAE/pregnancy CRFs, must be promptly reviewed, signed, and dated by the investigator or qualified physician who is a subinvestigator and who is delegated this task on the Delegation of Authority Form. For electronic CRFs, review and approval/signature is completed electronically through the BMS electronic data capture tool. The investigator must retain a copy of the CRFs including records of the changes and corrections.

Each individual electronically signing electronic CRFs must meet BMS training requirements and must only access the BMS electronic data capture tool using the unique user account provided by BMS. User accounts are not to be shared or reassigned to other individuals.

9.3 Clinical Study Report and Publications

A Signatory Investigator must be selected to sign the clinical study report.

For this protocol, the Signatory Investigator will be selected as appropriate based on the following criteria:

- External Principal Investigator designated at protocol development
- Subject recruitment (eg, among the top quartile of enrollers)
- Involvement in trial design
- Regional representation (eg, among top quartile of enrollers from a specified region or country)

The data collected during this study are confidential and proprietary to BMS. Any publications or abstracts arising from this study must adhere to the publication requirements set forth in the clinical trial agreement (CTA) governing [Study site or Investigator] participation in the study. These requirements include, but are not limited to, submitting proposed publications to BMS at the earliest practicable time prior to submission or presentation and otherwise within the time period set forth in the CTA.

10 GLOSSARY OF TERMS

Not applicable.

11 LIST OF ABBREVIATIONS

Term	Definition
ABC	Activated B cell like
ACTH	Adrenocorticotrophic Hormone
ACVBP	Doxorubicin, cyclophosphamide, vindesine, bleomycin and prednisone
ADC	Antibody-drug conjugate
AE	adverse event
AIDS	Acquired immunodeficiency syndrome
AITL	Angioimmunoblastic T Cell Lymphoma
ALCL	Anaplastic Large Cell Lymphoma
ALT	alanine aminotransferase
ANC	absolute neutrophil count
ASCT	Autologous Stem Cell Transplant
AST	aspartate aminotransferase
AT	Aminotransferase (ALT or AST)
BA	Bioavailability
BCNU	bis-chloroethylnitrosourea (Carmustine)
BE	Bioequivalence
BMI	body mass index
BMS	Bristol-Myers Squibb
BOR	best overall response
BP	blood pressure
BUN	blood urea nitrogen
BV	Brentuximab Vedotin
C	Celsius
Ca	Calcium
CBC	complete blood count
CFR	Code of Federal Regulations
CI	confidence interval
Cl	Chloride
CrCl	creatinine clearance

Term	Definition
CL/CLR	Clearance/renal clearance
Cm	Centimeter
CMV	Cytomegalovirus
CNS	Central nervous system
COO	Cell of Origin
CR	Complete remission
CRC	Colorectal Cancer
CrCl	Creatinine Clearance
CRF	Case Report Form, paper or electronic
CRR	Complete response rate
CT	Computed tomography
CTLA	Cytotoxic T-Lymphocyte Antigen
CTA	Clinical Trial Agreement
CTCAE	Common Terminology Criteria for Adverse Events
CTCL	Cutaneous T Cell Lymphoma
DILI	drug induced liver injury
dL	Deciliter
DLBCL	Diffuse large B-Cell lymphoma
DLT	Dose Limiting Toxicity
DOR	Duration of response
ECOG	Eastern Cooperative Oncology Group
eCRF	Electronic Case Report Form
EDC	Electronic Data Capture
EFS	Event Free Survival
eg	exempli gratia (for example)
ELISA	enzyme-linked immunosorbent assay
EORTC	European Organization of Research and Treatment of Cancer
ER	Endoplasmic Reticulum Stress
eSAE	Electronic Serious Adverse Event
ESR	Expedited Safety Report

Term	Definition
FDA	Food and Drug Administration
FDG	Fludeoxyglucose
FFPE	Formalin-Fixed Paraffin-Embedded
FSH	follicle stimulating hormone
g	Gram
GC	Germinal Center subtype
GCP	Good Clinical Practice
GGT	gamma-glutamyl transferase
GFR	glomerular filtration rate
G-CFS	Growth factor support
GVHD	Graft versus host disease
h	Hour
HBsAg	hepatitis B surface antigen
HBV	hepatitis B virus
HCG	Human chorionic gonadotropin
HCV	hepatitis C virus
HCO ₃ ⁻	Bicarbonate
HDACi	Histone deacetylase Inhibitor
HD-ASCT	High dose autologous stem cell transplant
HER2	Human epidermal growth factor receptor 2
HIPAA	Health Insurance Portability and Accountability Act
HIV	Human Immunodeficiency Virus
HL	Hodgkin lymphoma
HR	heart rate
HRT	hormone replacement therapy
HuMAb	Fully-human monoclonal antibody
IB	Investigational Brochure
ICD	Immunogenic cell death
ICR	Immune checkpoint receptors
ICH	International Conference on Harmonisation

Term	Definition
ICF	Informed Consent Form
ie	id est (that is)
IEC	Independent Ethics Committee
Ig	Immunoglobulin
IHC	Immunohistochemistry
IMP	investigational medicinal products
IND	Investigational New Drug
INN	International Nonproprietary Name
IPI	International prognostic index
IR	Indeterminate Response
IRB	Institutional Review Board
ISCL	International Society for Cutaneous Lymphoma
IU	International Unit
IUD	Intrauterine device
IV	Intravenous
IVRS	Interactive voice response system
JCV	John Cunningham virus
K+	Potassium
kg	Kilogram
L	Liter
LDH	lactate dehydrogenase
LFT	Liver function test
LPFT	Last Patient First Treatment
mAbs	monoclonal antibodies
mCRPC	Metastatic Castration-Resistance Prostate Cancer
MF	Mycosis Fungoides
mg	Milligram
Mg ⁺⁺	Magnesium
MGZL	Mediastinal Gray Zone Lymphoma
MHC	Major Histocompatibility Complex

Term	Definition
min	Minute
MRI	Magnetic resonance imaging
mL	Milliliter
MLR	mixed lymphocyte reaction
mm	Millimeter
MMAE	Monomethyl auristatin E
mmHg	millimeters of mercury
mSWAT	Modified Severity Weighted Tool
MTD	maximum tolerated dose
µg	Microgram
N	number of subjects or observations
Na	Sodium
N/A	not applicable
NCI-CTCAE	National Cancer Institute-Common Terminology Criteria for Adverse Events
NFκB	Natural Factor κB
ng	Nanogram
NIMP	non-investigational medicinal products
NIV	Nivolumab
NHL	Non-Hodgkin lymphoma
NK	Natural Killer
Non GC	Non germinal center subtype
NOS	Not otherwise specified
NSCLC	Non small cell lung cancer
ORR	Objective response rate
OS	Overall survival
PBMC	peripheral blood mononuclear cells
PD	Progressive Disease
PD-1	Programmed death-1 receptor
PET	Positron emission tomography

Term	Definition
PFS	Progression free survival
PK	pharmacokinetics
PPK	Population PK
PMBL	Primary Mediastinal B Lymphoma
PML	Progressive multifocal leukoencephalopathy
PR	Partial response
PRR	Partial response rate
PS	Performance Status
PTCL	Peripheral T Cell Lymphoma
q	Every
Q2W	Every 2 weeks
qPCR	Quantitative real-time polymerase chain reaction
RBC	red blood cell
RCC	Renal cell carcinoma
R-CHOP	Rituximab plus cyclophosphamide, doxorubicin, vincristine, prednisone/prednisolone
RO	Receptor Occupancy
RT-PCR	Reverse transcription- polymerase chain reaction
SAE	serious adverse event
SCT	Stem cell transplant
SD	Stable Disease
SmPC	Summary of product characteristics
SNP	Single nucleotide polymorphisms
SOP	Standard Operating Procedures
SS	Sézary Syndrome
t	temperature
T	time
TAO	Trial Access Online, the BMS implementation of an EDC capability
TCR	T-cell receptor
TFH	T Follicular helper cells

Term	Definition
T-HALF	Half life
TIL	tumor infiltrating lymphocytes
USAN	United States Adopted Name
USP	Unites States Pharmacopeia
ULN	upper limit of normal
WBC	white blood cell
WHO	World Health Organization
WOCBP	women of childbearing potential

APPENDIX 1 ECOG PERFORMANCE STATUS

ECOG PERFORMANCE STATUS	
0	Fully active, able to carry on all pre-disease performance without restriction
1	Restricted in physically strenuous activity but ambulatory and able to carry out work of a light or sedentary nature, eg, light house work, office work
2	Ambulatory and capable of all selfcare but unable to carry out any work activities. Up and about more than 50% of waking hours
3	Capable of only limited selfcare, confined to bed or chair more than 50% of waking hours
4	Completely disabled. Cannot carry on any selfcare. Totally confined to bed or chair
5	Dead

Toxicity and Response Criteria of the Eastern Cooperative Oncology Group.

APPENDIX 2 2014 LUGANO CLASSIFICATION: STAGING AND RESPONSE EVALUATION (DIFFUSE LARGE B CELL LYMPHOMA, PERIPHERAL T CELL LYMPHOMA, PRIMARY MEDIASTINAL B LYMPHOMA & MEDIASTINAL GRAY ZONE LYMPHOMA).

Table 1: Revised Criteria for Response Assessment

Response and Site	PET-CT–Based Response	CT-Based Response
Complete Lymph nodes and extralymphatic sites	Complete metabolic response Score 1, 2, or 3* with or without a residual mass on 5PS† It is recognized that in Waldeyer’s ring or extranodal sites with high physiologic uptake or with activation within spleen or marrow (eg, with chemotherapy or myeloid colony-stimulating factors), uptake may be greater than normal mediastinum and/or liver. In this circumstance, complete metabolic response may be inferred if uptake at sites of initial involvement is no greater than surrounding normal tissue even if the tissue has high physiologic uptake	Complete radiologic response (all of the following) Target nodes/nodal masses must regress to ≤ 1.5 cm in LDi No extralymphatic sites of disease
Nonmeasured lesion	Not applicable	Absent
Organ enlargement	Not applicable	Regress to normal
New lesions	None	None
Bone marrow	No evidence of FDG-avid disease in marrow	Normal by morphology, if indeterminate, IHC negative
Partial Lymph nodes and extralymphatic sites	Partial metabolic response Score 4 or 5† with reduced uptake compared with baseline and residual mass(es) of any size At interim, these findings suggest responding disease At end of treatment, these findings indicate residual disease	Partial remission (all of the following) ≥ 50% decrease in SPD of up to 6 target measurable nodes and extranodal sites When a lesion is too small to measure on CT, assign 5 mm × 5 mm as the default value When no longer visible, 0 × 0 mm For a node > 5 mm × 5 mm, but smaller than normal, use actual measurement for calculation
Nonmeasured lesions	Not applicable	Absent/normal, regressed, but no increase
Organ enlargement	Not applicable	Spleen must have regressed by > 50% in length beyond normal
New lesions	None	None
Bone marrow	Residual uptake higher than uptake in normal marrow but reduced compared with baseline (diffuse uptake compatible with reactive changes from chemotherapy allowed). If there are persistent focal changes in the marrow in the context of a nodal response, consideration should be given to further evaluation with MRI or biopsy or an interval scan	Not applicable
No response or stable disease Target nodes/nodal masses, extranodal lesions	No metabolic response Score 4 or 5 with no significant change in FDG uptake from baseline at interim or end of treatment	Stable disease < 50% decrease from baseline in SPD of up to 6 dominant, measurable nodes and extranodal sites; no criteria for progressive disease are met
Nonmeasured lesions	Not applicable	No increase consistent with progression
Organ enlargement	Not applicable	No increase consistent with progression
New lesions	None	None
Bone marrow	No change from baseline	Not applicable
Progressive disease Individual target nodes/nodal masses Extranodal lesions	Progressive metabolic disease Score 4 or 5 with an increase in intensity of uptake from baseline and/or New FDG-avid foci consistent with lymphoma at interim or end-of-treatment assessment	Progressive disease requires at least 1 of the following PPD progression: An individual node/lesion must be abnormal with: LDi > 1.5 cm and Increase by ≥ 50% from PPD nadir and An increase in LDi or SDi from nadir 0.5 cm for lesions ≤ 2 cm 1.0 cm for lesions > 2 cm In the setting of splenomegaly, the splenic length must increase by > 50% of the extent of its prior increase beyond baseline (eg, a 15-cm spleen must increase to > 16 cm). If no prior splenomegaly, must increase by at least 2 cm from baseline New or recurrent splenomegaly
Nonmeasured lesions	None	New or clear progression of preexisting nonmeasured lesions

(continued on following page)

Response and Site	PET-CT-Based Response	CT-Based Response
New lesions	New FDG-avid foci consistent with lymphoma rather than another etiology (eg, infection, inflammation). If uncertain regarding etiology of new lesions, biopsy or interval scan may be considered	Regrowth of previously resolved lesions A new node > 1.5 cm in any axis A new extranodal site > 1.0 cm in any axis; if < 1.0 cm in any axis, its presence must be unequivocal and must be attributable to lymphoma Assessable disease of any size unequivocally attributable to lymphoma
Bone marrow	New or recurrent FDG-avid foci	New or recurrent involvement

Abbreviations: 5PS, 5-point scale; CT, computed tomography; FDG, fluorodeoxyglucose; IHC, immunohistochemistry; LDi, longest transverse diameter of a lesion; MRI, magnetic resonance imaging; PET, positron emission tomography; PPD, cross product of the LDi and perpendicular diameter; SDi, shortest axis perpendicular to the LDi; SPD, sum of the product of the perpendicular diameters for multiple lesions.

*A score of 3 in many patients indicates a good prognosis with standard treatment, especially if at the time of an interim scan. However, in trials involving PET where de-escalation is investigated, it may be preferable to consider a score of 3 as inadequate response (to avoid undertreatment). Measured dominant lesions: Up to six of the largest dominant nodes, nodal masses, and extranodal lesions selected to be clearly measurable in two diameters. Nodes should preferably be from disparate regions of the body and should include, where applicable, mediastinal and retroperitoneal areas. Non-nodal lesions include those in solid organs (eg, liver, spleen, kidneys, lungs), GI involvement, cutaneous lesions, or those noted on palpation. Nonmeasured lesions: Any disease not selected as measured, dominant disease and truly assessable disease should be considered not measured. These sites include any nodes, nodal masses, and extranodal sites not selected as dominant or measurable or that do not meet the requirements for measurability but are still considered abnormal, as well as truly assessable disease, which is any site of suspected disease that would be difficult to follow quantitatively with measurement, including pleural effusions, ascites, bone lesions, leptomeningeal disease, abdominal masses, and other lesions that cannot be confirmed and followed by imaging. In Waldeyer's ring or in extranodal sites (eg, GI tract, liver, bone marrow), FDG uptake may be greater than in the mediastinum with complete metabolic response, but should be no higher than surrounding normal physiologic uptake (eg, with marrow activation as a result of chemotherapy or myeloid growth factors).

†PET 5PS: 1, no uptake above background; 2, uptake ≤ mediastinum; 3, uptake > mediastinum but ≤ liver; 4, uptake moderately > liver; 5, uptake markedly higher than liver and/or new lesions; X, new areas of uptake unlikely to be related to lymphoma.

*The recommendations from Lugano Classification is to use a 5 point scale to assess the metabolic response in PET-CT based response.

Response Evaluation in DLBCL, PTCL, PMBL & MGZL:

CR (Complete Remission)

The designation of CR requires all of the following be met:

- 1) Complete disappearance of all detectable clinical evidence of disease.
 - a) PET-CT-based response: A score of ≤ 3 is considered to represent complete metabolic response.
 - b) CT based response: Target node/nodal masses must regress to ≤ 1.5 cm in LDi, with no extralymphatic sites of disease.

Organ involvement: Absence of organomegaly (Table 3).

- 2) Bone marrow: No evidence of FDG-avid disease in marrow. If there was evidence of involvement of bone marrow with lymphoma at screening/baseline and a biopsy was performed (PTCL), a bone marrow biopsy will be required to confirm CR.
- 3) The presence of residual symptoms in the absence of detectable disease by imaging does not preclude the designation of CR.

PR (Partial Remission)

The designation of PR requires all of the following:

- 1) PET-CT based response: Score of 4 or 5, provided reduced uptake compared with base line and absence of structural progression development on CT Scan.

- 2) CT based response: $\geq 50\%$ regression in SPD of upto 6 measurable nodal and extranodal lesions (Table 3) .
- 3) Splenic and hepatic nodules must regress by $\geq 50\%$ in length beyond normal.

Bone marrow : reduced uptake compared with baseline. If there is evidence of nodal response but persistent focal changes in the marrow consider further evaluation (Table 3).

SD (Stable Disease)

SD is defined as the following:

- 1) PET-CT based response: no metabolic response, score of 4 or 5 with no significant changes from baseline.
- 2) CT based response: $< 50\%$ decrease from baseline, absence of new lesions (Table 3).
- 3) Bone marrow: no change from baseline.

PD: Relapsed Disease (after CR)/Progressive Disease (after PR, SD)

- 1) PET-CT based response: Score of 4 or 5 with increase in intensity from baseline or interim scan/ or any new FDG avid focus consistent with malignant lymphoma (Table 3).
- 2) CT based response: New node, new or recurrent splenomegaly, progression of existing lesions (Table 3).

IR (INDETERMINATE RESPONSE)

A patient will be considered to have Indeterminate Response (IR) in one or more of the 3 following circumstances

- 1) Increase in overall tumor burden (as assessed by SPD) of $\geq 50\%$ of up to 6 measurable lesions in the first 12 weeks of therapy, without clinical deterioration (IR(1))
- 2) Appearance of new lesions; or growth of one or more existing lesion(s) of $\geq 50\%$ at any time point during treatment occurring in the context of lack of overall progression ($<50\%$ increase) of overall tumor burden, as measured by SPD of up to 6 lesions at any time during the treatment (IR(2))
- 3) Increase in FDG uptake of one or more lesion(s) without a concomitant increase in lesion size or number (IR(3))

It is possible that, at a single time point a subject could fulfill criteria for both IR(1 or 2) AND IR(3): for example, there could be a new FDG-avid lesion in the absence of overall progression (IR(2)), and, at the same time, increase in FDG uptake of a separate lesion (IR(3)). In such cases, the designation of IR(1 or 2) should take priority (eg, IR(2))

Follow-up of IR

- 1) In patients categorized as having any of the above types of IR, it is mandatory to obtain a repeat imaging after an additional 12 weeks (or earlier if clinically indicated). At that time, response should be re-evaluated and the patient should be considered to have true PD if the SPD of target lesion has increased further, with the considerations below:
- 2) In the case of IR(1), the comparison should be between the first IR(1) and the current SPD, with an increase of >10% constituting PD. In addition there should be an increase of > 5 mm (in either dimension) of at least one lesion for lesions < 2 cm, and 10 mm for lesions > 2 cm, to be consistent with the Lugano classification (3)(Table 2). The 10% threshold is empiric but designed to account for variability in measurement (37), especially when taken along with the minimum increase. If the target SPD increase is < 10%, the response would still be categorized as IR(1), and the patient could continue treatment until a subsequent scan shows either true PD (> 10% increase from first IR(1) time point and an increase of > 5mm in either dimension of at least one lesion) or response (>50% decrease from baseline). In this situation, it is reasonable to repeat imaging in 4-8 weeks of the original IR(1) timepoint to ensure absence of significant further increase.
- 3) In the case of IR(2), the new or growing lesion(s) (unless biopsy proven to be benign) should be added to the target lesion(s), up to a total of no more than 6 total lesions. If the SPD of the newly defined set of target lesions has increased > 50% from the nadir value which may precede the IR time point. The patients is considered to have PD.
- 4) In the case of IR(3), since inflammatory responses may result in an increase in the standardized uptake value of a lesion, the patient will not be considered to have PD unless there is evidence of PD by an increase in lesion size or the development of new lesions, as noted above
- 5) Importantly, if a patient is assessed as having IR and then “true” PD at a subsequent time point (without an intervening objective response between IR and PD), the IR assessment should subsequently be corrected to PD for reporting purposes to the date of the prior designation of IR

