5.4 Efficacy Assessments

DLBCL, PTCL, PMBL and MGZL Efficacy Assessment:

The primary efficacy assessment is Objective Response (OR). Objective Response is defined as a subject achieving either a PR or CR according to the Lugano Classification 2014 and Lymphoma Response to Immunomodulatory therapy Criteria (LYRIC) ([Appendix 2](#)) and will be based on investigator assessed response. Efficacy assessment for DLBCL, PTCL, PMBL and MGZL will be primarily derived from the FDG PET-CT performed according to the timepoints described in [Table 5.1-1](#) [Table 5.1-2](#) and [Table 5.1-3](#). Subjects with PET-Avid lesions at baseline should be followed with PET, subjects with non-Pet avid lesions and lesions on CT scans at baseline should be followed with CT Scans. Tumor assessment (CR or non-CR) will be assessed by the investigator according to the Lugano Classification 2014.

CTCL Efficacy Assessment:

Efficacy assessment for Cutaneous T Cell lymphomas will include CT/MRI for visceral disease assessment and peripheral lymph nodes at the pre-determined timepoints described in [Table 5.1-1](#) [Table 5.1-2](#) and [Table 5.1-3](#). The consensus Global Response Score assessment to evaluate disease activity will also be completed at every tumor assessment time point to assess extent of disease. Medical photographs are recommended to document the appearance of skin lesions throughout the study. The mSWAT will be used to assess skin involvement, it is preferable that the mSWAT assessments should be performed by the same investigator at all time points to eliminate inter-

observer variability for a given patient. Lymphoma Response to Immunomodulatory therapy Criteria (LYRIC) will be used where clinically indicated ([Appendix 2](#)).

Whole blood must be included for assessment of SS-CTCL at baseline to evaluate blood tumor burden. In the case the blood is confirmed to be positive for tumor cells, it must be reassessed at the time of response documentation, prior to its confirmation.

All subjects treated are expected to be followed for disease progression. Subjects that discontinue treatment for other reasons different from disease progression must continue to perform tumor assessments as described in [Table 5.1-3](#) until disease progression is documented.

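### Appendix 2 defines partial response in two conflicting ways, so the same subject can be a responder or a non-responder in the primary ORR of the Lugano cohorts

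*Protocol*

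**What the plan says.** Protocol 8.3.1 and SAP 4.1 define the primary efficacy endpoint as ORR, based on best overall response (BOR) per Lugano 2014 in DLBCL, PTCL, PMBL and MGZL. Protocol 8.3.1 sends investigators to Appendix 2 for the criteria.

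Appendix 2 states those criteria twice.

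- **Table 1** has one column for PET-CT and one for CT. PET-CT PR is a score of 4 or 5 "with reduced uptake compared with baseline and residual mass(es) of any size". PET-CT CR is a score of 1 to 3 "with or without a residual mass on 5PS". Organ enlargement is marked not applicable in the PET-CT column for both. CT PR is at least a 50% "decrease in SPD of up to 6 target measurable nodes and extranodal sites", with no PET score needed.
- **The text after Table 1** says "The designation of PR requires all of the following" and numbers three items: "PET-CT based response: Score of 4 or 5, provided reduced uptake compared with base line and absence of structural progression development on CT Scan"; at least 50% "regression in SPD of upto 6 measurable nodal and extranodal lesions"; and splenic and hepatic regression. For CR it says "The designation of CR requires all of the following be met", with a PET sub-item (score 3 or lower), a CT sub-item (nodes down to 1.5 cm) and a line requiring no organomegaly.

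Protocol 5.4 and Table 5.1-2 set the imaging modality by baseline avidity: avid disease is followed with PET, while "subjects with non-Pet avid lesions and lesions on CT scans at baseline should be followed with CT Scans".

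**The concern.** Table 1 and the modality rule treat PET-CT and CT as separate routes to a response. The PR text joins them. No statement in the protocol or SAP says which governs, and SAP 4.1 cites Lugano 2014 without a rule for reaching BOR. The six table pointers in the text lead to Table 3, which is the mSWAT skin tool in Appendix 4, so they do not take the reader back to Table 1.

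Response is investigator-assessed in an open-label multicenter study (Protocol 3.1, 5.4), and central review of scans is at the sponsor's discretion (Protocol 5.3.1). No required step would bring sites that read the appendix differently to one answer. The ORR and CR rate of B1, B2, B4, B5 and the matching Cohort A subjects could then depend on which half of the appendix a site used.

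**Working it through.** **1. Classification under each version.** Assume no new lesions and no splenic or hepatic involvement.

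| Subject | Table 1, column for the modality followed | Appendix 2 text, read literally |
|---|---|---|
| 1. Avid, score 4, uptake reduced, SPD −30% | PR (PET-CT) | Not PR: the SPD item fails |
| 2. Non-avid, followed by CT, SPD −60% | PR (CT) | Not PR: no score of 4 or 5 |
| 3. Avid, score 2, SPD −60%, residual node 2.5 cm | CR (PET-CT) | Not CR if the CT sub-item binds; not PR, because the score is not 4 or 5 |
| 4. Avid, score 4, uptake reduced, SPD −60% | PR | PR |

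Subjects 1 and 2 are the firm cases. Subject 3 depends on how the CR sub-items are read.

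**2. The plan's own figures.** Inputs are from Protocol 8.1 and Table 8.1-1: one-sided alpha 0.10, with n, null p0 and target p1 by cohort. For B5 the planned observed rate is 30%, as in Table 8.1-1 and SAP 5.1. The threshold r is the smallest count with P(X ≥ r | n, p0) ≤ 0.10, and power is P(X ≥ r | n, p1).

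| Cohort | n | p0 | p1 | r | Attained alpha | Power | Stated |
|---|---|---|---|---|---|---|---|
| B1 | 40 | 0.40 | 0.60 | 21 | 0.074 | 87.0% | 87% |
| B2 | 30 | 0.40 | 0.60 | 16 | 0.097 | 82.5% | 82% |
| B4 | 30 | 0.30 | 0.50 | 13 | 0.084 | 81.9% | 81% |
| B5 | 10 | 0.10 | 0.30 | 3 | 0.070 | 61.7% | 61% |

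The stated powers reproduce to within one point.

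**3. How many reclassified responders change the conclusion.** Start from x = n × p1 responders. The number needed is x − r + 1. The lower limit L is the two-sided 80% Clopper-Pearson bound, which solves P(X ≥ x | n, L) = 0.10.

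| Cohort | Planned x (lower limit) | Needed | Count after (lower limit) | Null |
|---|---|---|---|---|
| B1 | 24/40 (48.6%) | 24 − 21 + 1 = 4 | 20/40 (38.8%) | 40% |
| B2 | 18/30 (46.7%) | 18 − 16 + 1 = 3 | 15/30 (37.0%) | 40% |
| B4 | 15/30 (37.0%) | 15 − 13 + 1 = 3 | 12/30 (27.7%) | 30% |
| B5 | 3/10 (11.6%) | 3 − 3 + 1 = 1 | 2/10 (5.5%) | 10% |

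As shares of responders these are 4/24 = 17%, 3/18 = 17%, 3/15 = 20% and 1/3 = 33%. One or two reclassifications leave B2 at 17 or 16 and B4 at 14 or 13, all still at or above threshold.

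**4. Sensitivity of power (assumption).** The documents give no rate of PET/CT disagreement. If the literal text removed a fraction f of responders, the true ORR would be p1 × (1 − f):

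| Cohort | f = 5% | f = 10% | f = 20% |
|---|---|---|---|
| B1 | 77% | 64% | 34% |
| B2 | 72% | 60% | 34% |
| B4 | 74% | 64% | 42% |
| B5 | 58% | 53% | 44% |

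**The case against.** The strongest reply is that the text only summarizes the table and nobody would read it as a checklist. Its items are labelled by modality, matching the two columns. PR item 1 already carries its own CT condition, no structural progression, which would have little to do if 50% SPD regression were also compulsory. The third CR item says residual symptoms do not rule out CR, so it is not a requirement at all, and the heading over that list cannot be fully literal. Protocol 5.4 assigns modality by avidity and makes FDG PET-CT the main source of efficacy data. BOR is the best designation recorded by the investigator, and neither document describes computing it from scores and SPD.

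Much of this stands as evidence of intent, and it favors Table 1. It does not remove the PR conflict: three numbered items sit under an explicit requirement for all of them, with no "or", and no sentence gives Table 1 precedence.

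It does limit the point in three places where a reader might go further.

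- **CR.** A reader might infer that CR is contradicted just as plainly. Its PET and CT criteria are lettered sub-items and can be read as modality routes. What clashes clearly is the heading and the unconditional organomegaly line, against a Table 1 PET-CT column that accepts a residual mass and marks organ enlargement not applicable.
- **Unclassifiable subjects.** A reader might infer that subject 1 fits no category. The stable disease text does not say that all its items are needed, and SPD −30% without new lesions meets its CT item. The subject moves from PR to SD.
- **Power loss.** A reader might infer falls to 68–44% (B1), 65–43% (B2) and 64–42% (B4). Those follow from taking 5 to 10 percentage points off ORR. Five points is already 5/60 = 8% of responders in B1 and B2, and 5/50 = 10% in B4. The documents support neither that loss nor the milder one in step 4.

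**Conclusion.** The concern holds for PR and, in weaker form, for CR. Appendix 2 contains two rules that give different primary-endpoint classifications for ordinary subjects, and the documents do not say which applies. The scope is B1, B2, B4, B5 and matching Cohort A subjects. CTCL uses the Global Response Score and is outside it.

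The firm measure of size is the margin at the planned observed rates: 4 responders in B1, 3 in B2, 3 in B4, 1 in B5. This rests only on the plan's sample sizes, nulls and interval method. How often subjects like 1 to 3 occur is unknown, so no expected loss of power can be claimed. Nor can a downward bias be taken as certain: it would arise only where sites apply the text literally, and only if Table 1 is the intended rule. The matter should be settled before ORR is analyzed because it sits in the definition of the primary endpoint and costs little to correct.

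**What to change.** - Reword the CR and PR text in Appendix 2 so that response is assigned by the modality set at baseline: the PET-CT column of Table 1 for PET-avid disease, the CT column for non-avid disease. This matches Table 1, Protocol 5.4 and Table 5.1-2.
- Point the six Table 3 references in that text to Table 1.
- State in SAP 4.1 that Table 1, by baseline modality, governs BOR in the Lugano cohorts.
- Reconcile this with Protocol 8.3.1 and SAP 4.1, which require a negative PET for any CR in these four diseases. A subject followed by CT only would otherwise meet the CT column for CR and still fail the endpoint definition. The documents need to say how such a subject is classified.
- Send sites a short memo and check responses already recorded against the single rule before the ORR analysis.

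The cost is a wording change in Appendix 2, a sentence in the SAP, the CR reconciliation in both documents and the check of recorded responses. No new assessments are needed.
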